
In designing a treatment that can be employed by PC-MHI providers, we considered several options but ultimately chose to modify the VA's full length CBT protocol³². First, CBT has the most well-established evidence base of psychotherapies for chronic pain^{31,33} and has therefore been rolled out extensively in VA. Second, a recent trial comparing CBT to another form of therapy for chronic pain, mindfulness-based stress reduction, found that the effect of these treatments is equivalent³⁴, indicating that mindfulness does not offer significant advantages over CBT. Third, six-session CBT for chronic pain groups have been shown to be cost effective for use in non-VA primary care³⁵, suggesting the potential of a briefer version of CBT in the primary care setting. Fourth, our prior work has shown that a clear majority of PC-MHI providers self-report use of CBT techniques as part of their routine practice to address other mental health conditions³⁶⁻³⁹. Nationally, some PCMHI providers play a role in delivering psychoeducational group interventions, or "pain schools", in primary care, yet the availability of these interventions is variable and the content is not standardized. Significantly, their overall effectiveness at improving patient outcomes appears marginal⁴⁰, suggesting that pain schools may be insufficient as the principal approach to addressing the psychosocial aspects of chronic pain. Therefore, a standardized protocol would capitalize on therapeutic elements that have demonstrated effectiveness, match well with the PC-MHI treatment platform, and address a significant concern among primary care patients.

Significance

The long term goal of this research is to promote recovery and psychological wellness among Veterans with chronic pain. The proposed study will advance knowledge in rehabilitation research by providing preliminary data regarding the feasibility and effectiveness of Brief CBT-CP as a front line treatment. More immediately, this pilot study will provide the necessary information to develop a proposal for a full scale effectiveness trial. This intervention has been designed specifically for PC-MHI providers and therefore has clear implications for translation to clinical practice. The potential direct benefit to Veterans includes offering a safe, accessible, evidence-based, non-pharmacological treatment for chronic pain early in the trajectory of VA care.

Research Design and Methods

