Conceptual framework. The biopsychosocial model of pain⁴¹ suggests that unchecked chronic pain can negatively impact activity engagement out of fear associated with movement. Limiting one's beneficial activities can result in physical deconditioning and avoidance of pleasurable events. Persistent pain and disengagement can lead to emotional distress and decreased motivation that result in further social/occupational role withdrawal. The subsequent state of disability is reinforced by maladaptive coping. Brief CBT-CP is aligned with this model and designed to target the biological (e.g., relaxation training), psychological (e.g., cognitive coping), and social (e.g., decreasing isolation) aspects of pain to improve long-term health outcomes. **Design** considerations and overview. This aim will evaluate the feasibility of Brief CBT-CP via a pilot randomized controlled trial (RCT). We will focus on feasibility outcomes because Brief CBT-CP has not been subject to prior research and documentation of the viability of study processes will provide critical information for future effectiveness studies⁴². We chose to randomize participants in order to have a realistic assessment of the stratified randomization procedure, retention of control participants, and assessment of the impact of our control condition on patient outcomes⁴³. Primary care treatment as usual (TAU) was chosen because the long term goal of developing Brief CBT-CP is to improve upon usual care practices of PACTs by adding a behavioral protocol for PC-MHI providers. We considered but excluded the use of a pain psychoeducation condition because this approach would not reflect true usual care practices at our study site (and many other VA primary care clinics). A psychoeducation control would need to be developed specifically for this trial and its use is not as well suited to our study question about whether Brief CBT-CP improves upon primary care TAU. A psychoeducation control is better suited to answering the question about the impact of specific CBT components above the impact of education and supportive contacts with a therapist.⁴⁴ Similarly, use of primary care TAU will best serve the goal of conducting a future effectiveness trial in real world primary care. 45 **Participants.** We will recruit 30 Veterans from the primary care clinics located at the Buffalo VAMC in Buffalo. NY. Thirty eligible participants will be randomized in a 1:1 ratio into either (1) Brief CBT-CP plus TAU or (2) TAU only. We will engage in recruitment during the second guarter of Year 1 through the end of the first quarter of Year 2. We aim to recruit and enroll 7-8 participants per quarter (or 2-3 patients per month) during that time frame. Post-treatment follow-up will be conducted at eight weeks and at 12 weeks.

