Patients will be excluded if chart review indicates either of the following: 1) unstable psychiatric status (e.g., active psychosis, current mania) or 2) major or minor neurocognitive disorder (e.g., dementia). Patients will also be excluded if chart review reveals uncontrolled medical conditions, scheduled/planned surgeries, and medical or other interventions likely to impact pain/functional ratings. Potential participants will not be excluded based on past/current/future use of chiropractic care or physical therapy.

Procedures. As shown in Figure 1, upon completing baseline measures, eligible participants will be randomly assigned to (1) Brief CBT-CP plus TAU or (2) TAU only. Assignment to Brief CBT-CP will be stratified based on degree of pain interference as measured by West Haven-Yale Multidimensional Pain Inventory – Interference (WHYMPI-I)⁵³. Participants will be classified as average interference and below (WHYMPI-I score ≤ 4.4) or as above average interference (WHYMPI-I score >4.4)^{28,53}. All participants will complete a telephone-based follow-up with the study coordinator, who will be blinded to participants' condition, at 8 weeks (post-test) and at 12 weeks (follow-up) from randomization for re-administration of study measures. Participants will be compensated \$40 for the initial assessment and \$30 for each of two follow ups (total \$100 for Aim 1). We will replace dropouts who do not meet minimum treatment completion requirements of attending ≥ 4 sessions. Attending, at minimum, sessions one through four will provide patients with essential education and core CBT self-management skills. Although some dropout is planned, we predict that we will replace only a small number of participants (~3-4) prior to our final 12-week follow-up assessment. This prediction is informed by [name] (Co-I) current clinical trial (IIR I01HX000909) of a brief behavioral intervention for depression conducted at the Buffalo VAMC primary care clinics which used similar methodology. At 90% completion, this study has evidenced only 11.3% participant drop out at 12-week follow-up.

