To assist with recruitment throughout the study, study staff will conduct reminder phone calls for all appointments 48-24 hours ahead of time reminding participants of the time and location of the meeting. Reminder letters containing date, location, and purpose of study contact will be sent prior to baseline, 8-week, and 12-week follow-up. Reminder letters will be sent for therapist appointments on an as-needed basis (e.g., when requested by participant). At least two phone attempts will be made (and one letter sent) to reach participants who do not show for scheduled contacts.

Participants will be provided with a behavioral health resource sheet at the end of their participation (or as needed during the trial) should they wish to access additional VA or community services.

Measures of feasibility. Our study measures focus on indicators of feasibility of trial processes^{43,54}. To assess feasibility of participant screening, recruitment, and retention, study staff will track the number of potential

participants identified by primary care team referral as well as our case finding procedure. We will document the number of potentially eligible participants who are sent study invitation letters, the number completing/refusing a screening call, and number who agree/refuse to be scheduled for baseline interview. We will track the number of participants who are randomized to compute actual enrollment rate (vs. planned enrollment), including time to reach full sample accrual. Within the Brief CBT-CP plus TAU condition, we will monitor treatment retention by assessing number of sessions attended, as well as the number of patients completing a full course of treatment. We will attempt to ascertain the reason for drop-out, when applicable,

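### Dropouts with fewer than 4 Brief CBT-CP sessions are to be replaced, but the plan does not say whether they stay in the attendance figures and the WHYMPI-I comparison, or how many people are randomised

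*Combined protocol and SAP*

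**What the plan says.** The replacement rule is under Procedures: "We will replace dropouts who do not meet minimum treatment completion requirements of attending ≥ 4 sessions". The same paragraph gives its expected extent: "we predict that we will replace only a small number of participants (~3-4) prior to our final 12-week follow-up assessment". The basis is a similar trial in the same clinics, of which the plan says "this study has evidenced only 11.3% participant drop out at 12-week follow-up".

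The number randomised appears under Participants, "Thirty eligible participants will be randomized in a 1:1 ratio into either (1) Brief CBT-CP plus TAU or (2) TAU only", and again as 30 under Sample size in the Aim 1 Analysis plan. Neither place mentions replacements. Aim 1 Study conditions gives six sessions to Brief CBT-CP and no PC-MHI behavioural intervention to TAU only.

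Three parts of the plan bear on who is counted:

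- Measures of feasibility, for the Brief CBT-CP arm: "we will monitor treatment retention by assessing number of sessions attended, as well as the number of patients completing a full course of treatment". No denominator is given.
- Primary feasibility outcomes defines the withdrawal rate over everyone randomised, and uses it to judge whether patients face barriers to treatment.
- Exploratory analysis of patient outcomes compares WHYMPI-I between conditions by baseline-adjusted ANCOVA, derives an effect size and plans multiple imputation. It names no analysis set.

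On follow-up, Procedures says "All participants will complete a telephone-based follow-up with the study coordinator" at 8 and 12 weeks.

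**The concern.** The rule acts on something that happens after randomisation, and it can operate in one arm only. If a replaced person is substituted out, the Brief CBT-CP arm becomes a group selected for attendance, while the TAU-only arm stays as randomised.

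Two results would be affected. The attendance and full-course figures would lose the people who did poorly on them. The WHYMPI-I effect size would compare attenders with all controls, which favours Brief CBT-CP if poor attenders also have worse outcomes.

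This matters more in a pilot than its size suggests, because feasibility is the main aim and, under Significance, "this pilot study will provide the necessary information to develop a proposal for a full scale effectiveness trial". A later trial planned on an inflated completion figure would expect better attendance than it will get.

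**Working it through.** Inputs from the documents: 30 randomised 1:1, so 15 per arm (Participants; Sample size); about 3 to 4 replacements and a cited dropout of 11.3% (Procedures); six sessions in Brief CBT-CP and none in TAU only (Aim 1 Study conditions). Assumed, and not in the documents: a correlation of 0.2 to 0.5 between attendance and outcome, and 12 full-course finishers in the worked example.

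1. **The plan's own forecast.** 30 × 0.113 = 3.39. Inflating for dropout, 30 / (1 − 0.113) = 33.8, rounded up to 34, which is 4 extra. The forecast of about 3 to 4 reproduces.

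2. **Total randomised.** One-for-one replacement by randomisation gives 30 + 3 = 33 or 30 + 4 = 34. So 30 cannot be the number randomised if the expected replacements are themselves randomised. Either 30 is the number left after substitution, or the total exceeds 30.

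3. **Full-course completion.** Let C be the number finishing all six sessions and k the number replaced. Nobody replaced is a finisher, so C is the same either way. With replaced people removed and all replacements entering Brief CBT-CP, the reported rate is C/15 instead of C/(15 + k), an inflation of (15 + k)/15. The range starts at k = 2 because the forecast may count dropout in both arms, and 15 × 0.113 = 1.70.

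| k | Inflation | Kept in, C = 12 | Removed, C = 12 |
|---|---|---|---|
| 2 | 17/15 = 1.13 | 12/17 = 71% | 12/15 = 80% |
| 3 | 18/15 = 1.20 | 12/18 = 67% | 12/15 = 80% |
| 4 | 19/15 = 1.27 | 12/19 = 63% | 12/15 = 80% |

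4. **If replacements are randomised 1:1 instead**, about half enter Brief CBT-CP. For k = 2, 15 + 1 = 16 are randomised to the arm and 14 remain: 16/14 = 1.14. For k = 4, 15 + 2 = 17 are randomised and 13 remain: 17/13 = 1.31. This takes the replacements to reach 4 sessions. The inflation comes from removing people, not from where the replacements go.

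5. **Effect size.** If the lowest-attending share p of the arm is removed, attendance and outcome are jointly normal with correlation ρ, and there is no true effect, the arm mean shifts by ρ × φ(z_p)/(1 − p) in SD units.
   - p = 2/17: 0.224ρ, or 0.04 to 0.11
   - p = 3/18: 0.300ρ, or 0.06 to 0.15
   - p = 4/19: 0.366ρ, or 0.07 to 0.18

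6. **Precision for comparison.** For an observed effect of zero with 15 per arm, the noncentral t limits are ±1.96 / √(15 × 15 / 30) = ±1.96 / 2.739 = ±0.716 SD.

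**The case against.** The strongest reply is that the plan already leans towards keeping everyone. All participants are to be followed from randomisation, reasons for dropout are sought on the follow-up calls, missing values are imputed, and the conditions are defined by assignment: "eligible participants will be randomly assigned to (1) Brief CBT-CP plus TAU or (2) TAU only". That sentence also suggests that replacements would be randomised. The attendance measures are counts rather than rates, the outcome analysis is labelled exploratory, and no sentence removes a replaced participant from anything.

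Much of this stands, and it rules out several stronger readings that a reader might infer:

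- *That nothing in the plan keeps replaced participants in the retention results.* The withdrawal rate under Primary feasibility outcomes is over all those randomised and, applied as written, includes them.
- *That the plan excludes them from the WHYMPI-I comparison.* It is silent. Follow-up of all participants plus imputation is compatible with including them.
- *That the forecast of 3 to 4 replacements is an error because the session rule reaches only about 15 people.* The forecast follows from 11.3% of 30 and may mean dropout in both arms.
- *That the inflation in the table is what will happen.* It is conditional on removal.

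What the reply does not settle is who is analysed and counted. Following people does not define an analysis set, and imputation works only within one. Counts become rates as soon as they are used to plan a trial, and these have no denominator. A fixed total of 30 beside planned replacements still points towards substitution.

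**Conclusion.** The point holds in limited form and should be fixed. Four things stand on the text: the replacement criterion is applied after randomisation and only one arm can fail it; the session-attendance and full-course figures have no denominator; the WHYMPI-I comparison has no named analysis set; and 30 randomised does not accommodate 3 to 4 randomised replacements.

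The consequence is conditional. If replaced participants are substituted out, full-course completion in Brief CBT-CP is overstated by a factor of 1.13 to 1.27, assuming 2 to 4 removed and all replacements in that arm. The effect-size bias of roughly 0.04 to 0.18 SD rests on an assumed correlation and is small against a half-width of about 0.72 SD, so the attendance figures are the main exposure. If everyone randomised is kept, neither problem arises.

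**What to change.** - In Procedures, Measures of feasibility and Exploratory analysis of patient outcomes, state that every randomised participant, including anyone replaced, is followed at 8 and 12 weeks, analysed in the assigned arm with the planned multiple imputation, and counted in the session-attendance and full-course denominators.
- State that additional participants are randomised 1:1 within the WHYMPI-I strata. Give the maximum number randomised (33 to 34 if 3 to 4 are replaced one for one) and align the totals under Participants and Sample size with it.
- Label any analysis limited to those attending at least 4 sessions as a sensitivity analysis.

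The cost is protocol wording, plus about 3 to 4 more people randomised if replacement is one for one. About half of them would go to TAU only, so slightly fewer treatment completers may contribute than under direct substitution. The reported completion figure may also look less favourable.

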
Eligibility and recruitment. Two recruitment methods will be used. Veterans with chronic musculoskeletal pain who self-report functional impairment will be referred by their PACT, in response to a recruitment flyer posted in primary care, or by contacting the PI or study staff directly after hearing of the study by word of

mouth or other sources, including ClinicalTrials.gov. This

[figure not shown]

Figure 1: Recruitment and procedures.

approach will be supplemented by a case-finding procedure in which study staff review electronic medical record data to identify potential patients. Initial eligibility criteria will target those Veterans who are age ≥18 years to 79 years, conversant in English, have an established history of VA primary care utilization (i.e., at least one primary care visit in the past year), and a diagnosis of musculoskeletal pain of ≥3 months. This pain definition is consistent with the consensus definition of chronic pain from the International Association for the Study of Pain^{46,47} and is well-matched to the study goal of addressing chronic pain proactively. Veterans meeting these initial eligibility criteria will be sent a study invitation letter signed by their primary care provider. Following the letter, Veterans will be contacted by phone for additional screening in which they will first be asked to verify the presence of current musculoskeletal pain for ≥ 3 months. The PEG^{48,49}, a validated 3-item pain measure^{48,49}, will also be administered. Veterans must score ≥4 on the PEG pain intensity item and ≥4 on either of the PEG pain interference items to be included. Veterans will be excluded at this stage if they self-report current engagement

in behavioral health services that may include cognitive or behavioral interventions (i.e., behavioral medicine intervention, specialty mental health services, or standard PC-MHI). Veterans receiving only psychopharmacological intervention from a mental health provider will not be excluded. Veterans will also be excluded if they report uncontrolled medical conditions, scheduled/planned surgeries, or other interventions likely to impact pain/functional outcome ratings. Potential participants will not be excluded based on past/current/future use of chiropractic care or physical therapy.

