In situations where the referring primary care provider and Veteran would rather directly connect to the study staff in-person, a letter will not be sent. Rather, and when feasible, study staff will be notified of the Veteran's preference to be screened at time of referral (or shortly thereafter) by study staff.

Veterans who meet telephone screening criteria will be scheduled for a face-to-face baseline interview. Following informed consent and HIPPA authorization procedures, assessment measures will be administered. Veterans will be screened for active suicidal ideation based on responses to the Patient Health Questionnaire9 (PHQ-9)⁵⁰. Veterans will be excluded from participation if they score >0 on PHQ-9 item 9 and also endorse imminent suicide risk (i.e., in response to additional questions that will differentiate suicide risk versus

nonsuicidal morbid ideation). Veterans will be excluded on the basis of probable substance use problems (e.g., alcohol, cannabis, opioids, benzodiazepines) if they score positive (≥8) on the Alcohol Use Disorders Identification Test⁵¹ (AUDIT) or score positive (≥3) on the Drug Abuse Screening Test⁵² (DAST-10). Veterans will also be excluded if their baseline administration of the BPI is <4 on the pain intensity items and <4 on pain interference items. Participants will also be excluded if they are unwilling to have their treatment sessions audio recorded.

Electronic medical record review will be used to identify if the patient is currently prescribed relevant pain or psychiatric medications. If relevant medications are prescribed, study staff will supplement this review by asking the patient to verbally verify if the medication(s) identified in the chart are 1) currently in use by the patient, 2) what the current schedule/frequency of use of that medication, and 3) if there have been changes in the past 2 months. Veterans will be excluded if relevant medications have been modified in the past 2 months. Use of over-the-counter (OTC) analgesic medications/topicals will not be considered an exclusion criterion, even if these agents are recorded in the patient's medical record by a VA provider. Similarly, routine or PRN use of prescribed anti-inflammatory medications (i.e., acetaminophen, aspirin, ibuprofen, naproxen) or topical agents will not be considered an exclusion criterion.

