Exploratory analysis of patient outcomes: Means, standard deviations, and confidence intervals (CIs) at each of the three measurement times per condition will be calculated. We will also generate a preliminary effect size at post-treatment and follow-up based on the WHYMPI – I. Effect sizes will be calculated by dividing the mean difference between intervention and control conditions by the pooled standard deviation. Then, 95% CIs will be calculated on the effect size by using the non-central *t*-distribution method⁶³. While this study is not adequately powered to detect small changes in patient outcomes, the mean WHYMPI-I score in each condition at post treatment will be compared (while adjusting for the baseline score) using analysis of co-variance (ANCOVA). Adjusting for baseline pain interference reduces the residual variance of the ANCOVA model thereby increasing power, and attributes potential differences between conditions at post treatment to the condition, not the baseline score (regression to the mean). Stratifying the randomization scheme according to baseline pain interference will also decrease the likelihood of regression to the mean, and using ANCOVA minimizes its effect at post treatment⁶⁴. A similar analysis will be conducted at follow-up and will be repeated with the remaining patient outcome measures. As an alternative to ANOCVA, we will also explore the use of multi-level modeling approaches. Multiple imputation will be used for any missing data⁶⁵. **Risks and data security** Potential Risks

Across study aims, one possible risk to participants is that of potential disclosure of sensitive information. Several steps will be taken to minimize risk of breaching confidentiality including educating research staff about confidentiality and ethical issues in regard to the study. All electronic and paper self-report data collected will be identified by a unique study identification number rather than individually identifiable information. Identifiable voice recordings will be stored separately and in accordance with the data security and privacy procedures below. Identifiable information for informed consent, payment, and enrollment status will be stored separately from study data and will also comply with the data security and privacy procedures. Data security and privacy procedures (below) are designed to minimize this risk.

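### The exploratory WHYMPI-I effect size leaves out the baseline adjustment already planned for the same outcome; with 15 per arm, including it would narrow the interval once baseline and outcome correlate above about 0.2

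*Combined protocol and SAP*

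**What the plan says.** Under Aim 1 Analysis plan, Exploratory analysis of patient outcomes, a preliminary effect size is planned for the WHYMPI-I at 8 and 12 weeks: "Effect sizes will be calculated by dividing the mean difference between intervention and control conditions by the pooled standard deviation". For the interval, the plan names its method: "95% CIs will be calculated on the effect size by using the non-central" version of the t distribution. Neither sentence mentions the baseline score.

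The next sentences of that section turn to a test of the same outcome. The condition means at post-treatment "will be compared (while adjusting for the baseline score) using analysis of co-variance (ANCOVA"), for this reason among others: "Adjusting for baseline pain interference reduces the residual variance of the ANCOVA model thereby increasing power". For 12 weeks, "A similar analysis will be conducted at follow-up". Nothing says that an effect size or its interval will be taken from the ANCOVA.

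Under Procedures, assignment "will be stratified based on degree of pain interference", with the WHYMPI-I cut at 4.4. Participants and Sample size give 30 participants randomised 1:1. The documents state no SD, expected effect, interval width or baseline-outcome correlation.

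**The concern.** The plan accepts the case for baseline adjustment when it tests the WHYMPI-I, but not when it estimates the size of the effect on it. The raw effect size leaves in outcome variation that the baseline score could explain. It also ignores a variable on which the randomisation was stratified. With 15 per arm the interval is wide in any case, so any precision available from data already collected is worth having. A raw effect size and an ANCOVA result can also diverge if baselines differ by chance, and the plan does not say which is the main estimate. What is at stake is the precision of one exploratory estimate of the primary patient outcome.

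**Working it through.** The plan states no power or interval width, so there is no figure of its own to reproduce.

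**Inputs.** N = 30, 15 per arm (Participants; Sample size). Degrees of freedom are 28 unadjusted and 27 with one covariate, so t = 2.048 and 2.052. Assumed: observed effect d = 0.5, and r from 0 to 0.7.

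**Step 1: the planned interval.** Inverting the non-central t distribution with 28 df at d = 0.5 gives -0.23 to 1.22, width 1.455.

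**Step 2: the same raw effect size with a simple delta-method interval.** Variance = 2/15 + d²/(2×28) = 0.1333 + 0.0045 = 0.1378; SE = 0.371. Width = 2 × 2.048 × 0.371 = 1.521. That is 1.521/1.455 = 1.045, or 4.5% wider than the planned interval before any adjustment. The difference comes from the type of interval.

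**Step 3: the adjusted effect size, divided by the raw pooled SD, with a delta-method interval.** Variance = (2/15)(1 − r²)(28/27) + d²/(2×28), with t on 27 df. At r = 0.5: 0.1333 × 0.75 × 1.037 + 0.0045 = 0.1082; SE = 0.329; width = 2 × 2.052 × 0.329 = 1.350.

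**Step 4: comparison.** The like-for-like column divides by 1.521, and the next column by the planned 1.455. The last two columns give the change in mean width for t-type intervals in simulation (40,000 trials per setting, true d = 0.5).

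| r | Adjusted width | Like for like | Versus planned CI | Simulated, simple randomisation | Simulated, stratified |
|---|---|---|---|---|---|
| 0 | 1.550 | +1.9% | +6.6% | +2.0% | +0.8% |
| 0.2 | 1.520 | 0.0% | +4.5% | 0.0% | −1.1% |
| 0.35 | 1.455 | −4.3% | 0.0% | −4.3% | −5.4% |
| 0.5 | 1.350 | −11.3% | −7.2% | −11.2% | −12.4% |
| 0.7 | 1.124 | −26.1% | −22.8% | −26.4% | −27.7% |

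Like for like, break-even is r = 0.20. With stratification it lies between 0.1 and 0.15 in this simulation. Against the planned interval, the delta-method version breaks even at r = 0.347, 0.351 and 0.358 for d = 0.2, 0.5 and 0.8.

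**Step 5: precision of the estimate and coverage under stratification** (8,000 runs per setting, blocks of 4, strata split 50/50 or 80/20, all assumed). Stratification already gives the raw estimate part of the benefit, so its SD falls by less than the interval narrows:
- r = 0.5: 0.356 to 0.338 (5% lower) with 50/50 strata, and 0.366 to 0.339 (7%) with 80/20.
- r = 0.7: 0.324 to 0.279 (14%) and 0.338 to 0.280 (17%).

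The planned interval does not credit that balance. Its coverage is 94.9-95.7% for r up to 0.3, 96.0-96.6% at r = 0.5 and 97.3-98.1% at r = 0.7. The adjusted delta-method interval covers 95.5-96.2% throughout.

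**Step 6: could entry rules lower r?** Under Eligibility and recruitment, "Veterans must score ≥4 on the PEG pain intensity item", and Veterans are "excluded if their baseline administration of the BPI is <4 on the pain intensity items" and likewise on interference. As an upper bound, suppose entry removed the lowest 20% to 50% of baseline WHYMPI-I directly. The baseline SD then shrinks by u = 0.764 to 0.603, and r becomes r·u/√(1 − r² + r²u²). An unselected 0.5 falls to 0.40 and 0.33 respectively. Like for like (Step 3 formula without the d² term, √[(1 − r²) × 28/27] × 2.052/2.048) the interval is still 6% and 4% narrower. Against the planned interval, the delta-method version is between 2% narrower and 1% wider.

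**The case against.** The strongest reply is that nothing is broken. The raw standardised difference is a standard measure, its interval method is named and suitable, and it compares easily with other studies. The ANCOVA already supplies an adjusted contrast; only its division by an SD and an interval for that ratio are missing. The correlation is unknown, and both the entry cut-offs and the move from a face-to-face baseline to telephone follow-up could lower it. Even at r = 0.7 the interval at d = 0.5 runs from −0.06 to 1.06, so the reading of the pilot would hardly change. The section itself calls the effect size preliminary and admits limited power.

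All of this stands, and it sets the importance of the point. It does not remove the gap, because no sentence takes an effect size or interval from the ANCOVA.

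Two stronger readings are tempting, and the documents do not support them. A reader might infer that the planned effect size is biased or its interval wrong. Randomisation protects the raw difference, and in the simulations coverage was about nominal or somewhat above. A reader might also infer that this estimate will set the sample size of the next trial. Significance says that the pilot as a whole will inform a full-scale proposal, but no section says that the effect size will be used in that way.

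**Conclusion.** The point holds as an optional improvement. Like for like, adjustment narrows the interval once r exceeds about 0.20, or about 0.1 to 0.2 with stratified randomisation. The size is 1-2% wider at r = 0, 4-5% narrower at r = 0.35, 11-12% at r = 0.5 and 26-28% at r = 0.7. These are average widths at 15 per arm with complete data. They rest on an assumed correlation and on dividing by the raw pooled SD.

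A reader who sets a delta-method interval beside the planned one might infer that adjustment helps only above r = 0.35. That figure belongs to the pair of intervals compared: 4.5% of width is lost by leaving the non-central t method, whether or not the estimate is adjusted.

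**What to change.** In Exploratory analysis of patient outcomes, name as the main exploratory effect size the ANCOVA baseline-adjusted mean difference divided by the raw pooled SD. The residual SD should not be used, because it defines a different and larger quantity. Give an interval that allows for estimating the SD. One option is variance = (ANCOVA SE / pooled SD)² + d²/(2×28), with t on 27 df for 30 complete cases. If that option is used, state that it is itself about 4.5% wider than the non-central t interval. Against the planned interval it is then narrower only above r of about 0.35: 7% wider at r = 0, 7% narrower at r = 0.5 and 23% narrower at r = 0.7. Keep the raw effect size with its non-central t interval as a descriptive line.

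Since missing data are to be multiply imputed, add that the estimate and this variance are pooled by Rubin's rules, with Barnard-Rubin degrees of freedom based on 27 complete-data df.

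The cost is two or three sentences and slightly more analysis work. The downside is a slightly wider interval if the correlation proves low.
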